6.2.1.4 Concomitant therapies

Relevant concomitant diagnoses and/or therapies present at trial entry and/or during Screening and relevant to the patient's safety during the trial as judged by the Investigator will be recorded in the eCRF (see [Section 4.2.2](#) for details on concomitant medications). Post-trial therapy for advanced or metastatic disease will also be documented.

6.2.2 Treatment period(s)

Please refer to [Schedule A Flow Chart](#) and [Schedule B Flow Chart](#) for a detailed presentation of each visit during the treatment period.

6.2.3 Follow up period and trial completion

6.2.3.1 End-of-treatment visit

The EOT visit will be performed after permanent discontinuation of trial medication for any reason, as soon as possible, but no later than 7 days after permanent discontinuation of the trial medication or when the Investigator decided with the patient to permanently discontinue the trial medication or became aware that the trial medication had been terminated.

After a decision to permanently discontinue treatment within the trial is taken, no further administration of study medication should take place and the EOT visit should be performed within 7 days of the decision. If the decision to permanently discontinue trial treatment is taken during a scheduled visit, the EOT visit should be performed instead of the scheduled visit.

6.2.3.2 Follow-up visit

A follow-up visit should be performed 42-49 days after the last administration of trial medication. The information collected at this visit should include all new AEs that occurred after EOT and a follow-up of AEs ongoing at EOT. Any subsequent anti-cancer therapy administered between EOT and follow-up should be reported.

Wherever possible the follow-up visit must be performed in person, but if the investigator judges appropriate (e.g. in the event the patient is undergoing end-of-life care), follow-up information may be collected by telephone.

The follow-up visit marks the completion of the study for the individual patient. After the completion of the study the patient will receive standard medical care.

7. STATISTICAL METHODS AND DETERMINATION OF SAMPLE SIZE

7.1 STATISTICAL DESIGN - MODEL

The trial will be performed as an open-label study. The objective of the design is to determine the MTD of BI 905681 defined as the highest dose with less than 25% risk of the true DLT rate being $\geq 33\%$ (EWOC criterion). The dose-finding in Schedule A and B will be guided by Bayesian 2-parameter logistic regression models with overdose control ([R13-4803](#)). Separate MTDs will be determined for Schedule A and Schedule B.

The model is given as follows:

$$\text{logit}(\pi_d) = \log(\alpha) + \beta * \log(d/d^*),$$

where $\text{logit}(\pi) = \log(\pi/(1-\pi))$.

π_d represents the probability of having a DLT in the MTD evaluation period at dose d , $d^* = 4.5 \text{ mg/kg/week}$ is the reference dose, allowing for the interpretation of α as the odds of a DLT at dose d^* , and $\theta = (\log(\alpha), \log(\beta))$ with $\alpha, \beta > 0$ is the parameter vector of the model.

The estimated probability of a DLT at each dose level from the model will be summarised using the following intervals:

Under dosing: [0.00, 0.16]

Targeted toxicity: [0.16, 0.33]

Over toxicity: [0.33, 1.00]

The BLRM recommended dose for the next dose level is the level with the posterior probability of the DLT rate falling in the target interval [0.16, 0.33] without skipping any dose level. Applying the EWOC criterion it should be unlikely (<25% posterior probability) that the DLT rate at that dose will exceed 0.33.

The MTD may be considered reached if all the following criteria are fulfilled:

1. Next recommended dose = current dose (stabilisation condition)
2. Number of DLTs in study is at least 1.
3. At least 9 patients have been treated in the trial.

and at least one of the following criteria is fulfilled:

- The posterior probability of the true DLT rate in the target interval [0.16 – 0.33] of the MTD is above 0.5, OR
- At least 6 patients have been treated at the MTD.

The SMC may recommend stopping the trial after the criterion for MTD is fulfilled. Further patients may be included to confirm this MTD estimate. If no DLT is observed while information from the PK profile is considered sufficient, the SMC may recommend a dose for further testing. Any DLTs occurring after the start of the second cycle will be considered for the evaluation of the recommended dose for further testing for BI 905681.

Since a Bayesian approach is applied, a prior distribution $f(\theta)$ for the unknown parameter vector θ needs to be specified.

This prior distribution will be specified as a mixture of three multivariate normal distributions, i.e.

$$a(\theta) = a_1 f_1(\theta) + a_2 f_2(\theta) + a_3 f_3(\theta)$$

with

$a_i, i = 1, 2, 3$ the prior mixture weights ($a_1 + a_2 + a_3 = 1$)

and

$$f_i(\theta) = \text{MVN}(\mu_i, \Sigma_i)$$

the multivariate normal distribution of the i -th component with mean vector μ_i and covariance matrix Σ_i , where

$$\Sigma_i = \begin{pmatrix} \sigma_{i,11}^2 & \sigma_{i,11}\sigma_{i,22}\rho_i \\ \sigma_{i,11}\sigma_{i,22}\rho_i & \sigma_{i,22}^2 \end{pmatrix}$$

Mixture prior distributions have the advantage that they allow for specification of different logistic dose-toxicity curves, therefore making the prior more robust.

Prior derivation (Schedule A):

For the current trial, no relevant information in the form of human data was available, since no trial in a comparable population with comparable dosing schedule has been conducted. To support the interpretation of the prior distribution, the highest dose is assumed to be 8.5 mg/kg/q3w. Therefore, the three mixture components were established as follows:

- A weakly informative prior was derived reflecting the a priori assumption that the median DLT rate at the starting dose of 1.0 mg/kg/q3w would equal 0.02, and the median DLT rate at the highest dose of 8.5 mg/kg/q3w would equal 0.1. This yields $\mu_1 = (-2.701, -0.233)$. The standard deviations were set such that large uncertainty about the parameter means is reflected, and the correlation was set to 0, thus yielding $\sigma_{1,11} = 2$, $\sigma_{1,22} = 1$ and $\rho_1 = 0$, respectively. The prior weight a_1 for the first component was chosen as 0.9.
- A high-toxicity weakly informative prior was derived reflecting the case that the compound would be much more toxic than expected. For this prior component, it was assumed that the median DLT rate at the starting dose of 1.0 mg/kg/q3w would equal 0.09, and the median DLT at the highest dose of 8.5 mg/kg/q3w would equal 0.40. These assumptions yield $\mu_2 = (-0.973, -0.115)$. The standard deviations and correlations were set identical to the weakly informative prior, i.e. $\sigma_{2,11} = 2$, $\sigma_{2,22} = 1$ and $\rho_2 = 0$, respectively. The prior weight a_2 for the second component was chosen as 0.05.
- A low-toxicity weakly informative prior was derived reflecting the case that the compound would be much less toxic than expected. For this prior component, it was assumed that the median DLT rate at the starting dose of 1.0 mg/kg/q3w would equal 0.01, and the median DLT at the highest dose of 8.5 mg/kg/q3w would equal 0.02. These assumptions yield $\mu_3 = (-4.101, -1.113)$, i.e. basically a flat curve. The standard deviations and correlations were set to $\sigma_{3,11} = 5$, $\sigma_{3,22} = 0.01$, therefore almost fixing

the slope parameter to its mean. The correlation was set to 0, i.e. $\rho_3 = 0$. The prior weight a_3 for the third component was chosen as 0.05.

A summary of the prior distribution is provided in [Table 7.1.1](#). Additionally, the prior probabilities of DLTs at different doses, as well as the corresponding probability of under-, targeted and overdosing, are shown in [Table 7.1: 2](#). Graphically, the prior medians with accompanying 95% credible intervals are shown in [Figure 7.1: 1](#). As can be seen from both, the table and the figure, the prior medians of the DLT probabilities are in-line with the prior medians derived from the weakly informative prior, and the uncertainty around the medians is large, showing the low amount of information this prior provides. This is also supported by the prior sample size, i.e., the information contained in the prior. This is approximately equal to 1.8 patients. A detailed evaluation of the model using hypothetical data scenarios and operating characteristics is provided in the statistical appendix (see [Appendix 10.3](#)).

Table 7.1: 1 Summary of prior distribution

[figure not shown]
Prior Component	Mixture Weight	Mean Vector	SD Vector	Correlation
1: Weakly inf.	0.9	-2.701,-0.233	2.000, 1.000	0.000
2: High Tox	0.05	-0.973,-0.115	2.000, 1.000	0.000
3: Low Tox	0.05	-4.101,-1.113	5.000, 0.010	0.000

Table 7.1: 2 Prior probabilities of DLT at selected doses

Dose	Probability of true DLT rate in			Mean	SD	Quantiles		
	[0-0.16)	[0.16-0.33)	[0.33-1]			2.50%	50%	97.50%
1	0.853	0.075	0.072	0.081	0.162	<0.001	0.014	0.637
2.5	0.780	0.106	0.114	0.118	0.191	<0.001	0.034	0.742
4.5	0.685	0.138	0.177	0.165	0.221	0.001	0.065	0.826
6.5	0.601	0.155	0.244	0.214	0.256	0.001	0.099	0.900
8.5	0.544	0.161	0.295	0.254	0.283	0.001	0.130	0.953

Doses printed in boldface meet the overdose criterion ($P(\text{overdose}) < 0.25$)

Figure 7.1: 1: Prior medians and 95% credible intervals

Prior derivation (Schedule B):

Schedule B will start after the MTD of Schedule A is reached and prior distribution of Schedule B will be derived based on the data observed from Schedule A.

Statistical model assessment:

The model is assessed based on two different metrics:

Hypothetical data scenarios: for various potential data constellations as they could occur in the actual trial, the maximal next doses as allowed by the model and by certain escalation limit are investigated. Various data scenarios provide a way to assess the “on-study” behaviour of the model.

Simulated operating characteristics: these illustrate how often a correct dose would be declared as MTD by the model for different assumed true dose-toxicity relationships. They can be considered as an assessment of the “long-run” behaviour of the model.

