In cases when DLT is not observed until the predicted efficacious dose 6.5 mg/kg/q3w, the adaptive feature of the model is fully illustrated in scenarios 7 to 10. Despite the fact that no DLTs were observed in the first three cohorts with 9 patients in total, the model reacts immediately to the data observed at 6.5 mg/kg/q3w and advises to stay at current dose in scenario with 1 observed DLT in scenario 8 and de-escalate with 2 observed DLTs in scenario 10. Further in scenario 9, one additional DLT is observed at 6.5mg/kg/q3w, the criteria of MTD are met and we claim MTD at 6.5 mg/kg/q3w.

Table 10.3:1 Hypothetical data scenarios for dosing Schedule A

Scenario	Dose (mg/kg/q3w)	# DLT	# Pat	Current Dose: P(OD)	Next Dose (mg/kg/q3w)	Next Dose		
						P(UD)	P(TD)	P(OD)
1	1	0		0.007	4.5	0.861	0.097	0.042
	2.5	0						
2	1	0		0.433	2.5	0.622	0.299	0.079
	2.5	0						
	4.5	2						
3	1	0		0.116	4.5	0.601	0.283	0.116
	2.5	0						
	4.5	1						
4	1	0		0.042	6.5	0.568	0.262	0.170
	2.5	0						
	4.5	1						
	4.5	0						
5	1	0		0.212	6.5	0.407	0.381	0.212
	2.5	0						
	4.5	1						
	4.5	0						
	6.5	1						
6	1	0		0.246	6.5	0.284	0.471	0.246
	2.5	0						
	4.5	1						
	4.5	0						
	6.5	1						
	6.5	1						
7	1	0		0.012	6.5	0.842	0.100	0.057
	2.5	0						
	4.5	0						
8	1	0		0.131	6.5	0.598	0.271	0.131
	2.5	0						
	4.5	0						
	6.5	1						
9	1	0		0.179	6.5	0.422	0.399	0.179
	2.5	0						
	4.5	0						
	6.5	2						
10	1	0		0.477	4.5	0.542	0.362	0.096
	2.5	0						
	4.5	0						
	6.5	2						

Operating characteristics

Operating characteristics are a way to assess the long-run behaviour of a model. Under an assumed true dose-toxicity curve, metrics such as the probability of recommending a dose with true DLT rate in the target interval can be approximated via simulation. In order to assess the operating characteristics of the model, we assume 5 true dose-toxicity scenarios. As is shown in [Table 10.3: 2](#), these scenarios reflect a wide range of possible cases as follows:

- Scenario 1: The true dose-toxicity relationship is aligned with prior means
- Scenario 2: High toxicity values are assumed corresponding to the respective dose levels
- Scenario 3: Low toxicity values are assumed corresponding to the respective dose levels
- Scenario 4: A non-logistic dose-toxicity relationship is assumed
- Scenario 5: Low toxicity values followed by high toxicity values are assumed, i.e. a very steep dose-toxicity curve is adopted.

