### **3. INTRODUCTION**

As per (1), the purpose of this document is to provide a more technical and detailed elaboration of the principal features of the analysis described in the protocol and to include detailed procedures for executing the statistical analysis of the primary and secondary variables and other data.

[figure not shown]
This Trial Statistical Analysis Plan (TSAP) assumes familiarity with the Clinical Trial Protocol (CTP), including Protocol Amendments. In particular, the TSAP is based on the planned analysis specification as written in CTP Section 7 “Statistical Methods and Determination of Sample Size”. Therefore, TSAP readers may consult the CTP for more background information on the study, e.g., on study objectives, study design and population, treatments, definition of measurements and variables, planning of sample size, and randomization.

Version 9.4 or the latest version will be used for analyses.

R Version 4.0.1 and JAGS Version 4.3.0 or the latest versions will be used for the Bayesian Logistic Regression Model (BLRM) analyses.

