## **4. CHANGES IN THE PLANNED ANALYSIS OF THE STUDY**

Due to enrollment issues, the trial will be terminated early without determination of the maximum tolerated dose (MTD)/optimal biologic dose (OBD) as per protocol. Only schedule A has been investigated in the trial. The early termination does not have an impact on the planned endpoints.

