## **7.4 PRIMARY ENDPOINT(S)**

### **7.4.1 Primary analysis of the primary endpoint(s)**

In order to identify the MTD of the trial, the number of patients at each dose level that had DLT during the MTD evaluation period (first three weeks for Schedule A) will be presented, excluding patients who discontinue during the first treatment cycle for reasons other than a DLT.

The BLRM as described in Section 7.1 of the CTP will be analyzed using the number of patients at each dose that had DLTs during the MTD evaluation period among the patients in the MTD set. The prior defined in Table 7.1: 1 of the CTP will be used for the analysis. The resulting posterior distribution of the DLT rates of the doses tested during the trial will be summarized using their mean, SD, 2.5% quantile, median, and 97.5% quantile. Additionally, the posterior probabilities of the DLT rate lying in the intervals [0, 0.16) (underdosing), [0.16, 0.33) (target dosing), and [0.33, 1] (overdosing) will be computed and listed for each dose. The posterior probabilities of underdosing, target dosing, and overdosing of the tested dose levels will additionally be visualized in a bar diagram that further displays which of the dose levels satisfy the EWOC criterion.

In addition, the number of patients with DLTs that occurred during the entire treatment period will be summarized at each dose level.

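### Protocol 7.1 gives the BLRM reference dose d* as 4.5 mg/kg/week, but the prior and tables were built on 4.5 mg/kg/q3w, and SAP 7.4.1 does not restate d*

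*Protocol*

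**What the plan says.** Protocol Section 7.1 defines the model as logit(π_d) = log(α) + β·log(d/d*), so that α is the odds of a DLT at d*. It gives d* the value 4.5 in a weekly unit: "mg/kg/week}$ is the reference dose, allowing for the interpretation of".

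The other doses feeding the Schedule A model are per three-week administration:

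- The first prior component is anchored at two q3w doses. For the lower one the assumption is: "the median DLT rate at the starting dose of 1.0 mg/kg/q3w would equal 0.02". The upper anchor is a rate of 0.1 at 8.5 mg/kg/q3w. The high- and low-toxicity components use the same two doses.
- For the prior, "the highest dose is assumed to be 8.5 mg/kg/q3w".
- The provisional levels in Table 4.1.3:1 (1.0, 2.5, 4.5, 6.5 and 8.5) and the scenarios in Appendix 10.3 are in mg/kg/q3w. On that scale, 4.5 is dose level 3.

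Global Amendment 1 revised Section 7.1 but lists no change to d*.

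SAP Section 7.4.1 takes the model from protocol Section 7.1 and adds: "The prior defined in Table 7.1: 1 of the CTP will be used for the analysis". Neither the value nor the unit of d* appears in the visible SAP text.

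**The concern.** The reference dose fixes what the intercept prior means, so d* is part of the primary-analysis model. The same prior mean for log(α) describes a different drug if d* moves.

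A weekly 4.5 converts to 4.5 × 3 = 13.5 mg/kg per three weeks. Keeping the printed prior with that value would place the assumed DLT odds at a dose beyond the tested range. Every tested dose would then look safer, and the EWOC limit (posterior P(DLT rate ≥ 0.33) below 0.25) would be easier to meet.

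The SAP programs the analysis afresh ("R Version 4.0.1 and JAGS Version 4.3.0 or the latest versions will be used") and points to Section 7.1 for the model. An analyst working from the text therefore meets the weekly unit as the only explicit statement of d*.

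**Working it through.** **1. Prior means (Table 7.1:1).** The inputs are the anchors in Section 7.1. For each component:

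- slope b = [logit(p at 8.5) − logit(p at 1.0)] / ln(8.5), with stated mean of log(β) = ln(b)
- intercept = logit(p at 1.0) + b·ln(d*)

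Component 1: b = [−2.197 − (−3.892)] / 2.140 = 0.792, and ln(b) = −0.233. With d* = 4.5 the intercept is −3.892 + 0.792 × 1.504 = −2.701, as printed.

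| Component | Anchors (1.0 / 8.5) | Printed means | d* = 4.5 q3w | Intercept if d* = 13.5 |
|---|---|---|---|---|
| 1 | 0.02 / 0.10 | −2.701, −0.233 | −2.701, −0.233 | −1.831 |
| 2 | 0.09 / 0.40 | −0.973, −0.115 | −0.973, −0.115 | 0.007 |
| 3 | 0.01 / 0.02 | −4.101, −1.113 | −4.101, −1.113 | −3.740 |

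Solving each printed intercept backwards, d* = exp[(intercept − logit(p at 1.0))/b], gives 4.50 three times. This step needs no assumption about cohort size. The reverse conversion (4.5/3 = 1.5) also fails, since component 1 would need −3.571.

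**2. Prior probabilities (Table 7.1:2).** The three-component mixture was integrated numerically on a grid, with the printed means, SDs and weights.

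| Dose (mg/kg) | Table P(overdose) | d* = 4.5 q3w | d* = 13.5, printed prior |
|---|---|---|---|
| 1.0 | 0.072 | 0.074 | 0.049 |
| 2.5 | 0.114 | 0.117 | 0.068 |
| 4.5 | 0.177 | 0.179 | 0.089 |
| 6.5 | 0.244 | 0.247 | 0.107 |
| 8.5 | 0.295 | 0.299 | 0.126 |

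With 4.5, all interval probabilities agree within 0.004. The prior median at 8.5 is 0.130 (table 0.130), against 0.039 with 13.5. Under 13.5 the 8.5 level would meet EWOC before any data, whereas the table has it failing.

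The direction is plain from component 1 at 8.5. With 4.5 the logit is −2.701 + 0.792·ln(8.5/4.5) = −2.197, a rate of 0.10. With 13.5 it is −2.701 + 0.792·ln(8.5/13.5) = −3.067, a rate of 0.044.

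**3. Data scenarios (Table 10.3:1).** The patient counts could not be read in the copy reviewed. Cohorts of three were assumed from the appendix narrative: "no DLTs were observed in the first three cohorts with 9 patients in total". Doses may not be skipped.

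With d* = 4.5 q3w, all ten next doses match and every current-dose P(overdose) is within 0.010:

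- Scenario 2 (two DLTs in three patients at 4.5): 0.426 (table 0.433); with 13.5, 0.230.
- Scenario 10 (two DLTs in three patients at 6.5): 0.468 (table 0.477); with 13.5, 0.174.

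Both would change from de-escalate to stay. Under 13.5 the recommended dose would rise in six of ten scenarios if the next dose is the permitted one with the largest P(target): 2, 3, 5, 8, 9 and 10. It would rise in seven if the highest permitted dose is taken. Scenario 6 is the extra one and is nearly tied under the first rule (P(target) 0.479 against 0.475). If the cohorts at 1.0 and 2.5 held two patients, scenario 2 would no longer move (P(overdose) 0.317), leaving five or six.

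**4. Final SAP analysis.** SAP Table 6.1:1 lists levels 1.0, 2.5, 5.0, 7.0 and 8.5. Prior P(overdose) at 7.0 is 0.262 with 4.5 and 0.112 with 13.5. For the posterior, assume three patients per level and no DLT below 8.5:

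| DLTs at 8.5 | P(overdose) at 8.5, d* = 4.5 q3w | d* = 13.5 | EWOC status at 8.5 |
|---|---|---|---|
| 0/3 | 0.006 | 0.001 | passes both ways |
| 1/3 | 0.077 | 0.022 | passes both ways |
| 2/3 | 0.336 | 0.128 | fails, then passes |
| 3/3 | 0.719 | 0.367 | fails both ways |

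In the 3/3 case the status changes one level down: at 7.0, P(overdose) is 0.434 with 4.5 and 0.205 with 13.5.

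**The case against.** The strongest reply is that this is a wrong label and that no calculation is wrong. The printed design results agree with 4.5 on the q3w scale, and entering the bare number 4.5 beside q3w doses gives the right model. Section 7.1 also contains the q3w anchors, the prior means and Table 7.1:2, which together determine d*. To reach 13.5 an analyst would have to convert one side unprompted, accept a reference dose above the top dose and overlook the table. That stands. It makes the error unlikely to have been carried into code, but it does not make the definition correct.

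The consequence is also limited by events. The trial is being "terminated early without determination of the maximum tolerated dose", Schedule B was not started, and two of the provisional levels behind the scenario counts (4.5 and 6.5) are not among those the SAP lists as administered. The scenario counts are therefore a measure of sensitivity only. They are not a claim about what happened. What remains is the SAP posterior summary and the EWOC bar diagram, which Section 7.4.1 still requires.

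Two caveats on the check itself are fair:

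- The match to Table 10.3:1 is not exact throughout. In scenario 10, P(underdose) and P(target) at the next dose come out at about 0.57–0.58 and 0.33–0.34, against the printed 0.542 and 0.362. The 13.5 reading fits that scenario far worse at the current dose (0.174 against 0.477).
- The SAP's silence on d* could be checked only in its visible text, because some sections are redacted.

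**Conclusion.** The concern holds. The unit of d* in protocol Section 7.1 contradicts the protocol's own prior and tables. The number 4.5 is consistent with them; the weekly unit is not. The proof is the exact agreement of the six prior means, which rests on no assumption. The agreement with Tables 7.1:2 and 10.3:1 supports it to within simulation-type error.

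The published design calculations are sound on the q3w scale. The harm is conditional on someone converting the unit while keeping the printed prior, and the documents do not show that this occurred. If it did, prior P(overdose) at 8.5 would fall from about 0.30 to 0.13. The EWOC status shown in the final analysis could change for some DLT outcomes, on the assumption of three patients per level and no DLT below 8.5.

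It should be corrected because it concerns a parameter of the primary-analysis model and the correction is almost free. It does not undermine the design.

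**What to change.** - In protocol Section 7.1, reconcile the unit of d* with the prior derivation and the tables (mg/kg/q3w, per administration).
- In SAP Section 7.4.1, add one sentence giving d* with its unit, so that the final analysis does not depend on the protocol wording.
- Confirm the d* coded in the R/JAGS program for both the escalation runs and the final posterior summary. Reproducing the 8.5 mg/kg row of Table 7.1:2 is enough: P(overdose) should be close to 0.295 and the median close to 0.130. A converted value would give about 0.126 and 0.039.

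The cost is one corrected unit, one SAP sentence and one short program check. With escalation over, the SAP sentence and the program check are the parts that still matter for the reported results.
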